- Screening and recruitment phone call: 30 minutes (in week 0)
- Information session (Zoom): 30 minutes (in week 0)
- Baduanjin mind-body exercise routine: approximately 30 minutes per day or 3 hours per week; (24 hours in total spaced across weeks 1 to 8)
- Completion of Exercise Logbook: approximately 10 minutes per week (1 hour and 20 minutes in total, spaced across the 8 weeks of the Baduanjin intervention)
- Telephone weekly check-ins: approx. 5 minutes per week (40 minutes in total)
- Outcome measures: 5-10 minutes each time (in week 0, week 4, week 8, and week 9) (Approximately 20 – 40 minutes in total) and
- Final week telephone call: 5- 10 minutes (in week 9)

Control Group (2 hours)

- Screening and recruitment phone call: 30 minutes (in week 0)
- Telephone weekly check-ins: approx. 5 minutes per week (40 minutes)
- Outcome measures: 5-10 minutes each time (in week 0, week 4, week 8, and week 9) (Approximately 20 – 40 minutes in total)
- Final week telephone call: 5- 10 minutes (in week 9)

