6.2 Study Procedure Risks

A systematic review identified 22 of 47 clinical trials (involving a total of 3877 participants) with (AE) reporting protocols, with only 2 trials subsequently reporting AEs potentially caused by Baduanjin mind-body exercise training [28]. There were no reported serious adverse events (SAE).

Baduanjin mind-body exercises may cause mild muscle soreness or stiffness during and after exercise in participant's who are physically unfamiliar with the prescribed movements. Physical mild soreness and stiffness usually ease shortly after the exercise session. However, this program is low in intensity, and has been structured with a warm-up and cool down phase to reduce this potential side effect.

There is the potential that side effects can be more serious [28]. Adverse reactions to professionally administered Baduanjin mind-body exercise have been reported and may include:

- Mild dizziness or drowsiness after treatment (rare).
- Mild chest pain, shortness of breath, cold sweats, nausea, and vomiting (very rare).

The study screening criteria excludes people with a known and uncontrolled health condition that might increase their risk of experiencing a rare or very rare adverse events. If fatigue begins to worsen (BFI is more than 8/10), the participant is advised to seek medical advice and may stop participation in the study's Baduanjin mind-body exercise. The Exercise Logbook also iterates instructions to inform the research team and stop and seek medical advice immediately if they experience any of the warning signs or symptoms noted.

Incorrect interpretation of Baduanjin mind-body exercise instructions might result in physical discomfort if the body movement is incorrectly executed. This potential risk will be minimised by having instructors who are experienced Baduanjin mind-body exercise instructors. Participants are additionally provided with daily Zoom support with instructors who can correct movements through demonstration and provide further clarity of exercise movements. Movements can be cross-referenced to the videos and brochure resources.

The Baduanjin Mind-Body Exercise Instruction Handbook also advises participants to stop exercise and seek medical attention immediately if they experience warning signs such as chest pain, shortness of breath, dizziness, cold sweats, nausea, or vomiting.

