Completing the study forms and outcome measures may pose some risk. While many of the questions are general, participants are being asked to reflect upon CRF because of a known cancer diagnosis or cancer-related fatigue that resulted from their cancer treatment. This might cause feelings of distress in some participants. Participants will be advised in the PIS of this and to consider their present health status.

The research takes place over a total of 10 weeks for both the intervention and control groups which may cause some inconvenience with participants time and to their usual established routines. However, for participants in the intervention group, the time for exercising is spaced and is limited to approximately 15 minutes twice a day for six days a week over 8 weeks (24 hours in total), undertaken online over Zoom, and is home-based. This minimises the time impact and inconvenience that would otherwise happen with traveling to a study site away from home. Additionally, the outcome measures are quick to complete. The BFI and PROMIS-29v2.0 together take approximately 10 minutes to complete. These are completed at four time points in the study, which is approximately 40 minutes for each study participant. Additionally, the intervention group participants each complete the Exercise Logbook which takes approximately 10 minutes each week (or 80 minutes in total across the 8 weeks of the intervention).

The study will use the WSU's Zoom subscription (available to Apple, Android devices and IBM) and configured security settings with password setting active to maintain secure links. The video recording feature will be automatically turned off. The Zoom app is free to download and easy to access through a mobile device or computer.

The nature of the study will not expose participants to illegal activity, and economic harm is not anticipated. Participants will have anticipated study-related internet usage costs covered (total of \$40). Participation in this study is voluntary and participants can withdraw at any time or stage of the research.

Given that there are no viable therapeutic options for CRF, the result of this research may provide a new therapeutic direction for CRF and improve the quality-of-life outcomes for people living with CRF. Hence, the benefit is justifiable considering the potential risks imposed.

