Each intervention group participant will receive an Exercise Logbook for reporting side effects of concern related to the Baduanjin mind-body exercise program. All Serious Adverse Events (SAEs) occurring between consent and the last visit for the study are recorded in detail in the Adverse Events Form by the member of the research team who received the original report, and who also informs the Principal Investigator. All AEs that occur between the first intervention and the last intervention for the study must be recorded in detail. In case of an AE/SAE, the Principal Investigator will initiate contact with appropriate members of the participant's health care team, or as according to their health care judgement given the nature of the AE/SAE. If necessary, participants will be withdrawn from the study. Participants with SAE/AEs present at the last intervention will be followed up until resolution of the event.

The SWSHLD Ethics Committee will be notified of any AE/SEA. Regular meetings will be scheduled by the Principal Investigator to discuss the AE with hospital clinicians. Participants will be provided a 24-hour contact number for any urgent matters or concerns. The severity, expectedness and causal relationship with the intervention will be assessed for every AE reported. The number and severity of AE, as recorded on an Adverse Events Form, will be reported in adherence to the requirements of the National Health and Medical Research Council for Clinical Trials Adverse Event Reporting.

Endpoints

Key feasibility endpoints are recruitment rates, and the participation and completion of the study interventions (from Logbook data) within the stated study periods. For feasibility and contributing to the design of a larger clinical trial, the primary outcome measure endpoint

will also include the effect of Baduanjin mind-body exercise on changes of fatigue as measured by the BFI score at baseline (week 0), at 4 weeks (mid-point), 8 weeks (final week) and 9 weeks (1 week follow-up) [29] (Additional secondary outcome measure endpoints will be the PROMIS-29v2.0 [28] and reported adverse events at baseline (week 0), 4 weeks, 8 weeks and 9 weeks (1 week follow-up) (Appendix 1. & Figure 1.) Participant's credibility and expectation ratings are compared prior to study group randomisation with their credibility scores on completing the Baduanjin mind-body exercise program.

Data analysis

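### Participants whom the team withdraws after an adverse event have no provision for their remaining BFI and PROMIS-29 assessments, so some as-randomised data may be lost (minor)

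*Protocol*

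**What the plan says.** Section 10 (Adverse Events Reporting and Management) gives the rule after an AE or SAE: "If necessary, participants will be withdrawn from the study". The follow-up attached to it concerns resolution of the event, for events still present at the last intervention. It does not mention BFI or PROMIS-29.

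Elsewhere the protocol separates stopping the exercise from leaving the study:

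- Section 6.2, BFI above 8/10: "the participant is advised to seek medical advice and may stop participation in the" exercise.
- Section 6.2, warning signs: the Handbook "also advises participants to stop exercise and seek medical attention immediately if they experience warning signs", and "The Exercise Logbook also iterates instructions to inform the research team and stop and seek medical advice immediately".
- Section 5.8: missed sessions do not count as deviations.

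The questionnaires are planned for all participants. Appendix 1 marks BFI and PROMIS-29 for everyone at weeks 0, 4, 8 and 9, and section 6.2 says "These are completed at four time points in the study, which is approximately 40 minutes for each study participant". Section 5.7 provides a revocation form for a participant's own decision to leave.

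Section 10 (Data analysis) plans an intention-to-treat analysis by randomised group alongside a per-protocol one, and uses the data to obtain an effect size for a larger study.

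**The concern.** The protocol fixes two things that fit poorly together. The analysis keeps everyone in the arm to which they were randomised, but the safety rule takes some people out of the study rather than out of the exercise. Read as written, the rule stops outcome collection for them. Values that were never collected cannot be recovered later, so a statistical analysis plan could only describe how to cope without them.

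BFI change is a secondary outcome in section 10, is added to the primary outcome endpoint under Endpoints, and is meant to inform the next trial. If those withdrawn have worse fatigue and come mainly from the exercise arm, the estimated benefit would look slightly too favourable.

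More frequent loss from the exercise arm is plausible. AEs are recorded between first and last intervention, and Appendix 1 marks AE assessment for that arm only. This remains an inference. SAEs are recorded from consent in both arms, and section 5.8 lists weekly calls for controls too, although Appendix 1 shows theirs only at weeks 0, 4, 8 and 9.

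**Working it through.** **Who is affected.**

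| Situation | Protocol's action | Are questionnaires expected to continue? |
|---|---|---|
| Missed sessions (5.8) | Not a deviation | Yes, as for everyone (Appendix 1) |
| BFI above 8/10, or warning signs (6.2) | Stop the exercise | Yes, by the same schedule; the person is still in the study |
| Participant decides to leave (5.7) | Revocation form | A decision of the participant |
| Team withdraws after AE/SAE (10) | Leaves the study | Not provided for |

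Only the last row is at issue.

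**The plan's own figures.** Section 5.3 gives n = 29 for 95% confidence of seeing an event of probability 0.10. This reproduces: 1 - 0.9^29 = 0.953, while 28 gives 0.948. Allowing for 15% attrition, 29/0.85 rounds up to 35, and 40 are recruited. With one to three people lost (39 to 37 left), the chance of seeing such an event stays at about 0.98. The sample-size statement is untouched.

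**Inputs for the size of the effect.**

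- From the protocol: 20 per arm, and 15% attrition, which is 0.15 x 20 = 3 in one arm.
- Assumed, because the protocol gives no figures: the withdrawn are d = 1 to 3 BFI points worse at week 8 than the rest of their arm; SD 2; equal within-person correlation rho of 0.5 to 0.7 between visits.
- kI and kC are the numbers withdrawn in the exercise and control arms.

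**Withdrawal before week 4.** Only baseline is observed and it does not show the worsening, so the mixed model cannot recover any of it:

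shift = ((kI - kC)/20) x d

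- kI = 1, kC = 0: 1/20 x 1 = 0.05 to 1/20 x 3 = 0.15.
- kI = 3, kC = 0: 3/20 x 1 = 0.15 to 3/20 x 3 = 0.45.
- kI = kC: 0. One control alone reverses the sign.

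**Withdrawal after week 4, worsening already visible there.** Given baseline and week 4 with equal correlation, the model predicts a fraction rho/(1 + rho) of the worsening at week 8: 0.5/1.5 = 33% to 0.7/1.7 = 41%. The remaining shift is the earlier one divided by (1 + rho).

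- kI = 1: 0.05/1.7 = 0.029 to 0.15/1.5 = 0.100.
- kI = 3: 0.15/1.7 = 0.088 to 0.45/1.5 = 0.300.

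Withdrawal after week 8 would cost only the week 9 values and leave the week 8 comparison intact.

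**Against the precision of the trial.** The 95% half-width of a 20-versus-20 difference is 1.96 x 2 x sqrt(2/20) = 1.24 points (0.62 SD).

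- One withdrawal: 0.029/1.24 = 2% to 0.15/1.24 = 12%.
- Extreme of three: at most 0.45/1.24 = 36%.

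**Loss of precision.** The standard error grows by sqrt(1/20 + 1/(20 - k))/sqrt(2/20), which is 1.013 for k = 1 and 1.043 for k = 3, or about 1% to 4%.

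**Feasibility rates.** Retention as written already requires 96 sessions, so anyone who stops early fails it in any case. Recruitment and adherence do not use these questionnaires.

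**The case against.** The strongest reply is that this is an ordinary last-resort safety clause which contradicts nothing. Intention to treat says which arm people are counted in and does not promise complete data. The common cases, worsening fatigue and warning signs, are already handled by stopping the exercise. Those left may be too ill to answer questionnaires, and the proposed exemption for harmful or impossible assessments would let many of them go again. Events from disease or chemotherapy can occur in either arm, so the direction of any bias is open. The review cited in section 6.2 found 22 trials with AE reporting, "with only 2 trials subsequently reporting AEs potentially caused by Baduanjin mind-body exercise training", and no serious events. The mixed model keeps earlier scores.

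Most of this stands, and it limits the size of the point. The affected group is small and may be empty, the direction is not established, and the 36% figure needs the whole attrition allowance in the exercise arm to be early team withdrawals, all 3 points worse.

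It does not close the gap. The rule as worded ends participation where stopping the exercise would often do, and no other section restores the assessments. The exemption still leaves people withdrawn because of the exercise who can answer an emailed form. The cited review concerns events potentially caused by Baduanjin, whereas the rule is not limited to related events. The attrition allowance protects numbers and gives no protection against selective loss.

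**Conclusion.** The concern holds, as a minor one. The protocol's wording allows scheduled outcomes to stop for people withdrawn by the team after an AE or SAE, which sits poorly with an analysis of everyone as randomised. The number of such people is unknown, and the effect is nil if there are none or if similar people are withdrawn equally in both arms. For a single exercise-arm withdrawal the week 8 BFI difference moves by roughly 0.03 to 0.15 points, well inside the trial's imprecision. The low end is more likely in view of the safety record the protocol cites. These sizes rest on the assumed worsening, SD and correlation, and a bias in favour of the exercise rests on unproven links with arm and fatigue. Only the pilot BFI and PROMIS-29 estimates could be affected.

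**What to change.** Replace the withdrawal sentence in section 10 with wording such as:

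> *If necessary, the exercise will be discontinued; the scheduled BFI, PROMIS-29 and AE/SAE contacts continue to week 9 unless the participant revokes consent or the investigator judges the assessments harmful or not possible.*

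Record exercise stopped for safety separately from leaving the study. In a trial of feasibility and acceptability that distinction is useful in itself. The clinical decision to stop the exercise stays with the investigators.

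The cost is a one-sentence amendment, one case report form field, and a small burden for the few people concerned. Section 5.8 puts the questionnaires at 5-10 minutes per occasion, completed online by emailed link, so three occasions (weeks 4, 8 and 9) come to at most 15-30 minutes, with no extra visits.

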1. SUMMARY

Study Title	Baduanjin mind-body exercise for cancer-related fatigue in cancer participants receiving adjuvant chemotherapy: a randomised control feasibility trial
Aims/Objectives	
Primary
 
The feasibility and acceptability of remotely delivered Baduanjin mind-body exercise (the study protocol) via recruitment, retention, and adherence rates.
 
Secondary
 
A reduction in the severity of cancer-related fatigue symptoms measured by the Brief Fatigue Inventory (BFI). The improvement in health domains relating to physical function, fatigue, pain interference, depressive symptoms, anxiety, ability to participate in social roles and activities, and sleep disturbance measured by PROMIS–29 Profile v2.0 and the number and severity of adverse events (AEs).
 
Participant’s ratings of the intervention before and after using a modified Credibility and Expectancy Questionnaire.
 
Reporting participation frequency via the Baduanjin Mind-Body Exercise Logbook.

Study design	Pilot randomised wait-list controlled feasibility trial
Planned sample size	40 (n = 20 per group)
Inclusion criteria	(1) 18 years of age or older; (2) receiving adjuvant chemotherapy or completed adjuvant chemotherapy; (3) medical history of cancer diagnosis; (4) suffering from moderate Cancer Related Fatigue (CRF) as assessed by the simple fatigue scale (from the BFI); (5) have a computer / device that is Wi-Fi or hotspot connected and be able to use smart phones, email and Zoom conferencing app; (6) be aware of one’s disease diagnosis; and (7) understand the intervention process and able to communicate and provide informed consent in English.
Study procedures	Eligible participants will be identified and referred by their treating oncologist, a health care team member or self-referral from advertising. The participants will be randomly assigned in a 1:1 ratio to the Baduanjin mind-body exercise or wait-list control groups respectively. Intervention group data will be collected at baseline (week 0), at 4 weeks, 8 weeks and one-week follow-up (week 9). Waitlist control group data will be collected at recruitment (week 0) and at week 4, week 8 and week 9 (follow-up).

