3. STUDY AIMS/OBJECTIVES

The primary study aim is to assess the feasibility and acceptability of a randomised controlled trial of a remotely delivered program of Baduanjin mind-body exercise with participants diagnosed with any type and stage of cancer and receiving or who have received chemotherapy, and who have identified as having CRF. Remote delivery refers to providing the program over the internet and using the video conferencing software Zoom.

The secondary objectives are to determine the effectiveness and safety of the remotely delivered Baduanjin mind-body exercise program for CRF, with consideration to the design of a larger scale clinical trial. The long-term goal is to contribute to the evidence base of interventions for CRF and improve the quality-of-life outcomes for people living with CRF.

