5.3 Data Source and Population

Participant's meeting study eligibility criteria will have their information collected using a study-specific Case Report Form. The form categories include demographic information (such as age, gender, ethnicity, language spoken at home), living arrangements, education and occupational status, and cancer type and treatment. (Refer to the Case Report Form).

The population are people diagnosed with any type and stage of cancer and receiving or who have received chemotherapy prior to study recruitment, and who have identified as having CRF.

To our knowledge, this will be the first study evaluating the feasibility and effects of Baduanjin mind-body exercise on cancer-related fatigue using a remote delivery method. Group sizes of 12 [26] and 15-20 per group are reported to give reasonable bias-corrected estimation of medium effect sizes in repeat-measure designed studies, as is being proposed for the current pilot [27]. For this pilot study, a sample size of $n = 29$ is necessary to have a 95% confidence of detecting an event which has a true probability of $\pi = 0.10$. To overcome the probable potential 15% participant attrition rate during the study [27] and to ensure availability of sufficient participants, a sample size of $n=40$ participants will be recruited in this study. Therefore, there will be 20 participants in the Baduanjin exercise, and another 20 participants in the control group. This number is sufficient to maximise

chances of identifying problems or feasibility issues that might arise with the intervention in preparation for a larger study [27].

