10. RESEARCH OUTCOMES

Primary outcome

Feasibility

- a). Recruitment rate: number of enquiries and number of enrolments per month of active recruitment; or
- b). Percentage conversion to enrolment measured as participants (n) enrolled / the total number of enquiries; and participants (n) enrolled / people (n) potentially eligible.
- c). Retention rate: participants (n) completing 8-week intervention (96 sessions) and outcome measures/ participants (n) enrolled.
- d). Adherence rate: participants (n) completing at least 80% or 10 out of 12 Baduanjin mind-body exercise days per week / total participants (n) allocated to the intervention group.

Secondary Outcomes (this will be done for calculating power for a larger study)

- a) Change (reduction) in the severity of cancer-related fatigue symptoms measured by the *Brief Fatigue Inventory* (BFI).
- b) Change (reduction) in any of health domains in physical function, fatigue, pain interference, depressive symptoms, anxiety, ability to participate in social roles and activities, and sleep disturbance measured by *PROMIS–29 Profile v2.0*.
- c) The number and severity of reported side effects and / or adverse events.
- d) Participant's perceptions of the Baduanjin (mind-body exercise) program before

randomization and after completion of the program as measured by the (modified) *Credibility and Expectancy Questionnaire*.

Outcome Measurements

Brief fatigue inventory (BFI)

The brief fatigue inventory is a validated measure sensitive to assessing patient reported fatigue [29]. It comprises nine items measured on a ten-point scale that assesses the severity of fatigue and its effects on the participant's ability in activities of daily living. A global fatigue score is calculated by averaging the score of the items. The BFI is short and easy to use (approximately 5 minutes to complete).

PROMIS-29 Profile v2.0

The Participant-Reported Outcomes Measurement Information System (PROMIS-29) v2.0 profile assesses pain intensity using a single 0–10 numeric rating item and seven health domains, (physical function, fatigue, pain interference, depressive symptoms, anxiety, ability to participate in social roles and activities, and sleep disturbance), using four items per domain [30]. It assesses health intervention impacts and tracks changes in health overtime [31]. It is a standard outcome reporting tool used in NSW Health.

Credibility and Expectancy Questionnaire

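### Feasibility is the primary aim, but no rate has a value that supports proceeding, changing or stopping, and two of the rates cannot be used as defined

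*Protocol*

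**What the plan says.** Section 3 sets the purpose: "The primary study aim is to assess the feasibility and acceptability of a randomised controlled trial of a remotely delivered program". The Summary says this will be judged "via recruitment, retention, and adherence rates". Section 5.3 presents the pilot as groundwork for a larger study.

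Section 10 lists the primary outcomes:

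- For recruitment, item (a) reads "Recruitment rate: number of enquiries and number of enrolments per month of active recruitment; or", and that last word leads to an alternative measure.
- The alternative, item (b), is "Percentage conversion to enrolment measured as participants (n) enrolled / the total number of enquiries", with a second version that divides by the potentially eligible.
- For retention, item (c) reads "Retention rate: participants (n) completing 8-week intervention (96 sessions) and outcome measures/ participants (n) enrolled".
- For adherence, item (d) takes the number of "participants (n) completing at least 80% or 10 out of 12 Baduanjin mind-body exercise days per week", divided by those allocated to the intervention.

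The Endpoints paragraph of the same section restates them: "Key feasibility endpoints are recruitment rates, and the participation and completion of the study interventions (from Logbook data) within the stated study periods".

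None of these places gives a target, a range or a decision rule. The Data analysis paragraph gives none either and refers to no other document for one. The sample-size text in section 5.3 mentions attrition only as a reason to enlarge the sample: "To overcome the probable potential 15% participant attrition rate during the study [27] and to ensure availability of sufficient participants".

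**The concern.** A feasibility trial is judged by what its rates mean for the next trial. Here the rates are named in advance, but the value that would count as adequate is not. Whoever writes the conclusion will pick that value with the results in view. Section 5.8 says that research-team members teach the exercise sessions, so that choice would not be made by a disinterested party.

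Two of the four rates also cannot be calculated sensibly as worded. Setting marks on them before repairing them would not help.

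**Working it through.** **Inputs from the protocol.** 40 participants, 20 per group (Summary). Two sessions a day, six days a week, eight weeks (section 5.8). n = 29 for 95% confidence of seeing an event of probability 0.10, and 15% attrition (section 5.3). Rate definitions (section 10).

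**Step 1: reproduce the planning figure and see what it covers.** n = ln(0.05)/ln(0.90) = 28.43, rounded up to 29. The chance of at least one event is 1 − 0.90^29 = 0.953. The figure reproduces. Allowing for 15% attrition, 29/0.85 = 34.1, so 35. The protocol goes to 40 to be sure of enough participants, and 40 × 0.85 = 34 still exceeds 29. This calculation concerns seeing a problem at least once. It sets no standard for any primary rate.

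**Step 2: check the figures that might be taken for a pass mark.**

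| Figure | What it does |
|---|---|
| 80%, or 10 of 12 | Classifies one participant as adherent; silent on how many of 20 must be |
| 15% attrition | Sample-size allowance |
| n = 29 | Chance of seeing a problem once |
| 40 participants, trial period to December 2024 | Plan, not tied to a verdict |

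**Step 3: check the definitions.**

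- *Retention (c).* Full attendance is 2 × 6 × 8 = 96 sessions, available only to the 20 intervention participants; section 5.8 gives controls no exercise during the study. With all 40 enrolled in the denominator, the literal maximum is 20/40 = 50%.
- *Adherence (d).* Twelve is the number of sessions in a week (2 × 6), so 10 of 12 days a week is impossible with six exercise days. Also 10/12 = 83.3%, and 80% of 12 = 9.6. Rounding up to 10 would explain one week, but over eight weeks the two readings differ: 80% of 96 is 76.8 sessions, against 10 × 8 = 80.
- *Recruitment (a) or (b).* The connecting word leaves open which measure counts.

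**Step 4: how much the choice of mark matters.** The marks and true rates below are assumptions, because the protocol gives none. For adherence, n = 20 and X ~ Binomial(20, p):

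| Mark | Needed | Pass if true rate 50% | 60% | 80% |
|---|---|---|---|---|
| 50% | 10/20 | 0.588 | 0.872 | 0.999 |
| 60% | 12/20 | 0.252 | 0.596 | 0.990 |
| 70% | 14/20 | 0.058 | 0.250 | 0.913 |
| 80% | 16/20 | 0.006 | 0.051 | 0.630 |

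The data will not settle the matter. An observed 14/20 has an exact (Clopper-Pearson) 95% interval of 0.457 to 0.881, which contains 50%, 60%, 70% and 80%.

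**Step 5: retention, once redefined.** Suppose retention is week-8 outcome data in both arms over all 40 randomised. This is not the protocol's present quantity. With X ~ Binomial(40, p):

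| Go mark | Pass if true rate 60% | 70% | 85% |
|---|---|---|---|
| 28/40 (70%) | 0.129 | 0.577 | 0.996 |
| 32/40 (80%) | 0.006 | 0.111 | 0.865 |
| 34/40 (85%) | 0.001 | 0.024 | 0.607 |

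A mark set exactly at the planning figure is missed about 39% of the time by a trial that performs as planned.

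**The case against.** The strongest reply is that the protocol never promises a yes/no verdict. It speaks of assessing feasibility, finding problems, and supplying data to power and shape a later trial. On that reading the rates are estimates, and an estimate needs no pass mark. A statistical analysis plan that is not shown might also hold criteria.

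Part of this stands. A reader might infer that the trial cannot answer its primary question, or that a poor result would launch the larger trial. The documents support neither: no binary decision is promised, and no text makes the larger trial conditional on these rates. A reader might also infer that any result at all could be called feasible. That goes too far. The measures are listed in advance, a participant-level adherence cut-off exists, and falling short of 40 participants by December 2024 would be visible.

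The rest does not stand. The protocol does not say that the rates are for estimation only, and its sample size is not justified by the precision of any of them. What result supports moving on belongs with the primary outcome, and section 10 neither states it nor refers elsewhere for it. The faulty definitions are in the protocol's own text whatever another document says.

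It is also fair to say that different cut-offs give different answers in any trial. That is the reason to fix them beforehand.

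**Conclusion.** The point holds in this form: the feasibility conclusion would depend on a mark chosen after the rates are known, and the definitions of retention and adherence must be made workable before any mark is set.

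The size depends on assumed marks and true rates. If true adherence is 60%, the chance of passing runs from 87% with a 50% mark to 5% with an 80% mark. The retention ceiling of 20/40 and the mismatch between days and sessions rest on no assumption beyond the protocol's own schedule and planned numbers.

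Two tempting inferences should be avoided. The 15% attrition allowance is not a retention target, so 85% is not a standard that the protocol has set itself. Pass probabilities for retention out of 40 do not describe the rate as now defined; they apply only after it is redefined.

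**What to change.** Amend section 10 before outcome data are reviewed:

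1. **Definitions.** Define retention as participants in both arms who provide week-8 outcome measures, divided by all randomised. State adherence in sessions per week with a single threshold, and reconcile it with the schedule in section 5.8.
2. **Zones.** Set go, modify and not-feasible ranges for retention, adherence and recruitment. For recruitment, choose enrolment pace or conversion in place of the present either/or, and name the denominator if it is conversion. The sponsor should choose and justify the cut-offs and show their operating characteristics, as in the tables above. Because 34/40 is reached only about 61% of the time when true retention is 85%, a go mark below the planning figure may be preferred.
3. **Actions.** State what follows from each combination of zones, including that any rate in the not-feasible zone means that the larger trial does not proceed in this form.
4. **Reporting.** Give each rate that is a proportion with its exact 95% binomial CI, and enrolments per month, if chosen, with an exact Poisson interval.

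The cost is a short protocol amendment, with no added participants, visits or data. The downsides are that the trial can visibly miss its mark and that the zones are coarse: one participant is 5 percentage points at n = 20 and 2.5 at n = 40. The middle zone is there to absorb that.
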